6.1.4. Prior and Concomitant Medications

The percentages of participants who started taking at least 1 concomitant medication, by type (any, antipyretic), from Day 1 to Day 14 after study intervention administrations will be tabulated by group with the exact 95% CI.

The percentages of participants who started taking at least 1 concomitant medication, by type (any, antipyretic), within 1 month after each dose will also be tabulated by group with exact 95% CI.

6.1.5. Study Intervention Compliance

The number of doses administered will be tabulated for each group for the ES. A dose is defined as a vaccination visit. Accordingly, a visit at which a replacement dose was given following regurgitation will be counted as one dose.

6.1.6. Reactogenicity/Safety Compliance

The number and percentage of participants with symptom sheets returned with documented occurrence of at least one solicited symptom will be tabulated by group and by dose for the ES.

6.2. Appendix 2 Data Derivations Rule

6.2.1. Study Day and Reference Dates

The reference day is defined as the day of 1st vaccine dose.

The study day is calculated as below:

- Assessment Date = Missing → Study Day = Missing
- Assessment Date < Reference Date → Study Day = Assessment Date – Ref Date
- Assessment Date ≥ Reference Date → Study Day = Assessment Date – Ref Date + 1

6.2.2. Assessment Window

Table 4 Intervals between study visits for Co-administration group

Interval	Optimal interval	Allowed interval range	Allowed interval during special circumstances [#]
Visit 1→Visit 2	15 days	14-18 days between study enrolment and Dose 1 of IPV and Rotarix PCV-free	14-45 days
Visit 2→Visit 4	30 days	28-36 [†] days between Dose 1 of IPV and Rotarix PCV-free and Dose 2 of IPV and Rotarix PCV-free	28-60 days
Visit 4→Visit 6	30 days	28-36 [†] days between Dose 2 of IPV and Rotarix PCV-free and Dose 3 of IPV and BS for assessment of Rotavirus Ab, IgA	28-60 days
Visit 6→Visit 7	30 days	30-36 [†] days between Dose 3 of IPV and BS for assessment of anti-poliovirus types 1, 2 and 3 Ab	30-60 days

Ab: Antibody; BS: Blood sampling; IgA: Immunoglobulin A; IPV: Inactivated poliovirus vaccine; PCV: Porcine circovirus; PCV-free: no detection of PCV-1 and PCV-2 according to the limit of detection of the tests used

[†] Participants will not be eligible for inclusion in the Per Protocol Set for immunogenicity if they make the study visit outside this interval. Interval is computed as the difference between the 2 dates of the study procedure.

[#] Refer to Section 8 of the protocol for more details on special circumstances (e.g., COVID-19 pandemic).

Table 5 Intervals between study visits for Staggered group

Interval	Optimal interval	Allowed interval range	Allowed interval during special circumstances [#]
Visit 1→Visit 2	15 days	14-18 [†] days between Dose 1 of Rotarix PCV-free and Dose 1 of IPV	14-45 days
Visit 1→Visit 3	30 days	28-36 [†] days between Dose 1 and Dose 2 of Rotarix PCV-free	28-60 days
Visit 2→Visit 4	30 days	28-36 [†] days between Dose 1 and Dose 2 of IPV	28-60 days
Visit 3→Visit 5	30 days	28-36 [†] days between Dose 2 of Rotarix PCV-free and BS for assessment of Rotavirus Ab, IgA	28-60 days
Visit 4→Visit 6	30 days	28-36 [†] days between Dose 2 and Dose 3 of IPV	28-60 days
Visit 6→Visit 7	30 days	30-36 [†] days between Dose 3 of IPV and BS for assessment of anti-poliovirus types 1, 2 and 3 Ab	30-60 days

Ab: Antibody; BS: Blood sampling; IgA: Immunoglobulin A; IPV: Inactivated poliovirus vaccine; PCV: *Porcine circovirus*; PCV-free: no detection of PCV-1 and PCV-2 according to the limit of detection of the tests used

† Participants may not be eligible for inclusion in the Per Protocol Set for immunogenicity if they make the study visit outside this interval. Interval is computed as the difference between the 2 dates of the study procedure.

Refer to Section 8 for more details on special circumstances (e.g., COVID-19 pandemic).

6.2.3. Handling of partial or missing Dates

Element	Reporting Detail											
General	
 Partial dates will be displayed as captured in participant listing displays. When partially completed dates (i.e. with missing day or month) are used in calculations, the following standard rules will be applied: 
 a missing day will be replaced by 15 a missing day and month will be replaced by June 30th. Derivations for partial dates for Adverse Events, concomitant medication/medical history and age are detailed below 											
Adverse Events	
The general rules above apply, with the following exceptions for missing start day/ missing start day and month.
 
 
 Missing start day	If the event starts in the same month as at least 1 of the study doses, the contents of AE.AESTRTPT (the flag indicating if the event occurred before or after vaccination) will be used to complete the date. If 'after vaccination' is selected, the imputed start date will match the first (or only) study dose given during that month. If 'before vaccination' is selected, the imputed date will be 1 day before the first (or only) study dose given during that month.	
 
 Missing start day and month	If the event starts in the same year as at least 1 of the study doses, the contents of AE.AESTRTPT (the flag indicating if the event occurred before or after vaccination) will be used to complete the date. If 'after vaccination' is selected, the imputed start date will match the first (or only) study dose given during that year. If 'before vaccination' is selected, the imputed date will be 1 day before the first (or only) study dose given during that year.	
 
 Missing end day	The general rule is applied	
 
 Missing end day and month	The general rule is applied	
 
 Completely missing start/end date	No imputation	
 
		Missing start day	If the event starts in the same month as at least 1 of the study doses, the contents of AE.AESTRTPT (the flag indicating if the event occurred before or after vaccination) will be used to complete the date. If 'after vaccination' is selected, the imputed start date will match the first (or only) study dose given during that month. If 'before vaccination' is selected, the imputed date will be 1 day before the first (or only) study dose given during that month.	Missing start day and month	If the event starts in the same year as at least 1 of the study doses, the contents of AE.AESTRTPT (the flag indicating if the event occurred before or after vaccination) will be used to complete the date. If 'after vaccination' is selected, the imputed start date will match the first (or only) study dose given during that year. If 'before vaccination' is selected, the imputed date will be 1 day before the first (or only) study dose given during that year.	Missing end day	The general rule is applied	Missing end day and month	The general rule is applied	Completely missing start/end date	No imputation
Missing start day	If the event starts in the same month as at least 1 of the study doses, the contents of AE.AESTRTPT (the flag indicating if the event occurred before or after vaccination) will be used to complete the date. If 'after vaccination' is selected, the imputed start date will match the first (or only) study dose given during that month. If 'before vaccination' is selected, the imputed date will be 1 day before the first (or only) study dose given during that month.											
Missing start day and month	If the event starts in the same year as at least 1 of the study doses, the contents of AE.AESTRTPT (the flag indicating if the event occurred before or after vaccination) will be used to complete the date. If 'after vaccination' is selected, the imputed start date will match the first (or only) study dose given during that year. If 'before vaccination' is selected, the imputed date will be 1 day before the first (or only) study dose given during that year.											
Missing end day	The general rule is applied											
Missing end day and month	The general rule is applied											
Completely missing start/end date	No imputation											
Concomitant Medications/Medical History	
The general rules above apply,
 
 
 Missing start day	The general rule is applied	
 
 Missing start day and month	The general rule is applied	
 
 Missing end day	The general rule is applied	
 
 Missing end day and month	The general rule is applied	
 
		Missing start day	The general rule is applied	Missing start day and month	The general rule is applied	Missing end day	The general rule is applied	Missing end day and month	The general rule is applied		
Missing start day	The general rule is applied											
Missing start day and month	The general rule is applied											
Missing end day	The general rule is applied											
Missing end day and month	The general rule is applied											

Element	Reporting Detail	
	Completely missing start/end date	No imputation

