4. STUDY DESIGN

4.1. Overall design

The study design is presented in [Figure 1](#).

Figure 1 Study design overview

AE: Adverse Event; IPV: Inactivated poliovirus vaccine; PCV: *Porcine circovirus*; PCV-free: no detection of PCV-1 and PCV-2 according to the limit of detection of the tests used; SAE: Serious Adverse Event; N: Total number of participants planned to be enrolled; n: Planned number of participants in each group.

Study interventions: IPV (Co-administered vaccine) and *Rotarix* PCV-free (Study vaccine).

[§] Refer to the Schedule of activities (SoA; Section 1.3) for Co-administration group. Note: For the Co-administration group, unsolicited AEs will be collected from visit 2 till visit 6.

+ Visit not applicable for participants in the Co-administration group.

[^] Blood sampling to be done before study intervention administration.

° Blood sample for anti-poliovirus types 1, 2 and 3 antibodies measurement.

* Blood sample for anti-RV IgA antibody measurement.

- **Experimental design:** Phase III, open-label, randomized, controlled study with 2 groups (see [Figure 1](#)).
- **Duration of the study:** The total duration of the study, per participant, will be approximately 3.5 months.
- **Control:** active comparator, i.e., staggered administration of licensed IPV and *Rotarix* PCV-free.
- **Blinding:** Open-label. Refer to Section [6.3.4](#) for details.
- **Data collection:** Standardized electronic Case Report Form (eCRF). Solicited systemic events will be collected using a diary card. Refer to Section [10.3.6.1](#) for details on recording and follow-up of SAEs.
- **Primary Completion Date (PCD):** Visit 7 (Month 3.5).
- **End of Study (EoS):** EoS is defined as last subject last visit (LSLV) (Visit 7) or date of the last testing/reading released of the Human Biological Samples, related to primary and secondary endpoints, whichever occurs later. EoS must be achieved no later than 8 months after LSLV. EoS cannot be before LSLV. Refer to Section [4.4](#) for details.

Table 6 Study groups, intervention and blinding

Study groups	Number of participants	Age (Min-Max)	Study interventions	Blinding
Co-administration	200	6-10 weeks*	IPV, Rotarix PCV-free	Open-label
Staggered	200	6-10 weeks*	IPV, Rotarix PCV-free	Open-label

IPV: Inactivated poliovirus vaccine; Max: maximum; Min: minimum; PCV: *Porcine circovirus*

* 6-10 weeks at the time of study enrolment

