
 To evaluate the reactogenicity of Rotarix PCV-free and IPV in terms of solicited systemic events. To assess the safety of Rotarix PCV-free in terms of unsolicited AEs and serious adverse events (SAEs) and safety of IPV in terms of SAEs. 	
 Solicited AEs 
 For each solicited systemic event, percentage of participants reporting the occurrence of the event within 14 days (Day 1- Day 14) after Dose 1 and Dose 2 of Rotarix and IPV Unsolicited AEs 
 Percentage of participants reporting the occurrence of unsolicited AEs within 31 days (Day 1- Day 31) after each dose of Rotarix, according to the MedDRA classification. SAEs: 
 Percentage of participants reporting SAEs from the first dose of the study intervention up to study end in the Co-administration and Staggered groups.

Ab: Antibody; GMC: Geometric mean Ab concentration; GMT: Geometric mean Ab titer; IgA: Immunoglobulin A; IPV: Inactivated poliovirus vaccine; MedDRA: Medical Dictionary for Regulatory Activities; mL: milliliter; PCV: *Porcine circovirus*; SAE: Serious Adverse Event; U: Unit

*Seroconversion rate for IPV neutralizing Ab is defined as percentage of participants with

[figure not shown]
- Titer $\geq 1:8$ at 1 month after 3 dose primary schedule of IPV in participants with titer $<1:8$ pre-vaccination
- Titer ≥ 4 -fold increase in titer 1 month after 3 dose primary vaccination schedule in participants with titer $\geq 1:8$ pre-vaccination.

Note: the 4-fold increase will take into consideration the expected decline in maternal antibodies with estimated half-life of 28 days.

**Seroconversion rate for anti-RV IgA Ab is defined as the percentage of participants who were initially seronegative (i.e., with anti-RV IgA Ab concentration <20 U/mL prior the first dose of *Rotarix*) and developed anti-RV IgA Ab concentration ≥ 20 U/mL at 1 month post Dose 2.

** complementary details on estimand including impact of intercurrent events on the analysis is available in Section 3 and Section 4.

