4.5. Safety Analyses

The analyses will be descriptive and conducted on the ES.

The following calculations will be performed for each group:

- The percentage of doses and participants reporting at least 1 AE (solicited or unsolicited) during the 14-day (Day 1 to Day 14) solicited follow-up period will be computed, along with exact 95% CI. The same calculations will be done for AEs (solicited or unsolicited) rated as grade 3 in intensity and for AEs leading to a medically attended visit.
- The percentage of doses over the study and the percentage of participants (by dose and over the study) reporting each individual solicited systemic event will be computed, over the 14-day (Day 1 to Day 14) solicited follow-up period, following study intervention administration, along with exact 95% CI. The same calculations will be done for each individual solicited systemic event rated as grade 3 (grade 3 or grade 4 for fever) in intensity and events leading to a medically attended visit. Temperature above specific thresholds will also be summarized with threshold defined by half degree increment.

Note: Intensity of fever will be assessed by considering the grading scales recommended by the Chinese authorities [NMPA, 2019].

- The verbatim reports of unsolicited AEs will be reviewed by a physician and will be coded according to MedDRA. Every verbatim term will be matched with the appropriate Preferred Term. The percentage of participants with unsolicited AEs occurring within 31-day (Day 1 to Day 31) follow-up period after any dose of *Rotarix* PCV-free with its exact 95% CI will be tabulated by Preferred Term. The same calculations will be done for each AE rated as grade 3 in intensity, for AEs leading to a medically attended visit and for AEs causally related to HRV as per the investigator assessment.
- The percentage of participants reporting the occurrence of SAEs (any, related, fatal, fatal related) from Dose 1 of the study intervention up to study end with its exact 95% CI will be tabulated by study group and by preferred term.
- The percentage of participants reporting the occurrence of SAEs (any, related, fatal, fatal related) within 31-day (Day 1 to Day 31) follow-up period after any dose with its exact 95% CI will be tabulated by study group and by preferred term.
- SAEs and dropouts due to AEs will be described in detail.

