6.2.6. Onset day

The onset day for an event (e.g., AE, medication, vaccination) is the number of days between the last study vaccination and the start date of the event. This is 1 for an event occurring on the same day as a vaccination (and reported as starting after vaccination).

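### The AE partial-date rule in SAP 6.2.3 ignores vaccine product and recorded end date, so it can give impossible start dates and move unsolicited AEs out of the Rotarix Day 1-31 window

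*SAP*

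**What the plan says.** SAP 6.2.3 (Adverse Events, missing start day) applies "If the event starts in the same month as at least 1 of the study doses". Any study dose triggers it, Rotarix PCV-free or IPV. With the flag set to after vaccination, "the imputed start date will match the first (or only) study dose given during that month". With the flag set to before vaccination, "the imputed date will be 1 day before the first (or only) study dose given during that month". If no dose falls in the month, the general rule applies: "a missing day will be replaced by 15". The section does not say which vaccination the flag refers to, and it has no check against the end date or the visit at which the event was reported.

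The endpoint is specific to one product. SAP 1.1 defines it as "Percentage of participants reporting the occurrence of unsolicited AEs within 31 days (Day 1- Day 31) after each dose of" Rotarix, and SAP 4.5 as "The percentage of participants with unsolicited AEs occurring within 31-day (Day 1 to Day 31) follow-up period after any dose of" Rotarix PCV-free. Protocol 4.2 makes Visit 6 (Month 2.5) an IPV-only visit in both groups. On collection, the Figure 1 note in Protocol 4.1 adds: "For the Co-administration group, unsolicited AEs will be collected from visit 2 till visit 6". SAP 6.2.6 defines onset day as "the number of days between the last study vaccination and the start date of the event", again for any product.

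**The concern.** The imputation works on any dose, while the endpoint window works on Rotarix only. Suppose an infant has an AE some weeks after Rotarix Dose 2, the parent recalls only the month, and the only dose in that month is IPV Dose 3. The rule then places the start at Visit 6, or the day before it. That date can lie beyond Rotarix Day 31 although the event began inside the window, and it can lie after the recorded end.

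Two things are at stake: events missing from a secondary safety table, and records whose start is later than their end. The loss also differs by group, because Visit 6 follows Rotarix Dose 2 by about 30 days in Co-administration and about 45 days in Staggered.

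**Working it through.** The plan gives no figure for this point, so there is none to reproduce.

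**Inputs.** Intervals are from SAP Tables 4 and 5 (same as Protocol Tables 3 and 4): Visit 1 to 2, 14-18 days (optimal 15); Visit 1 to 3, Visit 2 to 4 and Visit 4 to 6, each 28-36 days (optimal 30). An interval is the difference between two dates. The dose date is Day 1 (SAP 6.2.6), so Day 31 is dose date + 30.

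**Where Visit 6 falls relative to Rotarix Dose 2**

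- Co-administration: Rotarix Dose 2 is at Visit 4. With a Visit 4-to-6 gap of g days, Visit 6 is Day g + 1. It is outside the window when g + 1 > 31, that is g = 31-36 (Day 32-37). The day before Visit 6 is Day g, outside when g = 32-36.
- Staggered: Rotarix Dose 2 is at Visit 3. The gap from Visit 3 to Visit 6 is (V1 to V2) + (V2 to V4) + (V4 to V6) - (V1 to V3). Minimum 14 + 28 + 28 - 36 = 34 days; optimal 15 + 30 + 30 - 30 = 45; maximum 18 + 36 + 36 - 28 = 62. Visit 6 is therefore Day 35-63, always outside.

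**Worked example, Staggered, optimal spacing.** Rotarix Dose 2 on 5 May, IPV Dose 2 on 20 May, IPV Dose 3 on 19 June. An AE is recorded as starting in June and ending on 4 June, so its true onset was 1-4 June (Day 28-31). The after branch gives 19 June: Day 46, and 15 days after the event ended. The before branch gives 18 June: Day 45, still impossible and still outside.

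**Worked example, Co-administration.** Rotarix Dose 2 on 10 March, true onset 3 April (Day 25), day missing, flag after. Gap 30: dated 9 April, Day 31, inside. Gap 31: dated 10 April, Day 32, outside. Gap 33: dated 12 April, Day 34, outside.

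**Share moved out.** Assumptions, none of them in the documents: dose dates uniform over 366 days, true onset uniform over Days 1-31 after Rotarix Dose 2, start day missing, other visits at optimal spacing, flag read as after the first study vaccination.

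| Visit 4-to-6 gap (days) | Co-administration | Staggered, total | Staggered, via Visit 6 |
|---|---|---|---|
| 28 | 0.3% | 12.7% | 12.7% |
| 29 | 0.1% | 12.7% | 12.7% |
| 30 | 0.0% | 12.6% | 12.6% |
| 31 | 47.6% | 12.0% | 11.9% |
| 32 | 44.5% | 11.1% | 10.4% |
| 33 | 41.5% | 11.1% | 8.9% |
| 34 | 38.6% | 11.1% | 7.6% |
| 35 | 35.8% | 11.1% | 6.4% |
| 36 | 33.1% | 11.1% | 5.3% |

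The rest of the Staggered total comes from the day-15 fallback. If the flag is read relative to that month's dose, Co-administration is also about 0% at 31 days and unchanged at 32-36; Staggered stays at 11-13%.

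**Events after Rotarix Dose 1** are not moved out under the first-vaccination reading: a date matched to Rotarix Dose 2 is Day 1 of that dose. Under the other reading this holds when the Rotarix doses are at most 31 days apart. At 32-36 days, the day before Dose 2 is Day 32-36 after Dose 1.

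**Scale.** Suppose 1-3% of AEs lack a start day and half of all AEs follow Dose 2. Unsolicited AEs in one arm needed to lose one:

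- Staggered at 30 days: 1 / (0.03 x 0.126 / 2) = about 530, or about 1,590 at 1%.
- Co-administration at 31 days, its worst gap: 1 / (0.03 x 0.476 / 2) = about 140, or about 420 at 1%. At 30 days none is lost.

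**The case against.** The strongest reply is that this hardly matters. Under Protocol 10.3.4, site staff document reported events in detail, and the remainder are collected by interview and record review at the next visit, so missing days may be rare. The endpoint is descriptive, no between-group AE comparison is planned, and an infant with another in-window AE still counts in the any-AE row. All of this stands and keeps the point minor. It does not make a start date 15 days after the end date acceptable.

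Three stronger readings are tempting and should not be drawn.

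- A reader might infer that the rule flatters Co-administration. At gaps of 31-36 days that group loses more (33-48% against 11-12%), but at the optimal 30 days the order reverses (0% against about 13%). The documents give no distribution of gaps.
- A reader might infer that every displaced AE truly belonged in the window. The Figure 1 note runs Co-administration collection to Visit 6, which is Day 32-37 at gaps of 31-36 days. AEs leading to withdrawal are recorded through Visit 7. Some events dated outside may really be outside.
- A reader might infer from SAP 6.2.6 that any event dated to Visit 6 is lost to IPV whatever the gap. SAP 4.5 defines the window by Rotarix dose and does not refer to 6.2.6; at 30 days such events sit on Day 31, inside.

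**Conclusion.** The defect is in the text and survives either reading of the flag: followed as written, SAP 6.2.3 can give a start after the recorded end and can move an in-window event out of the Rotarix window. The effect is confined to AEs with a known month and a missing day. The percentages are shares of those events only, after Rotarix Dose 2, and rest on uniform dates and onsets. Misclassification differs by arm, but its net direction is not established. The documents give neither the number of unsolicited AEs nor the rate of missing days, so a count of affected infants cannot be derived; it is probably very small. This is a low-priority correction to a descriptive secondary safety endpoint. The primary non-inferiority test is unaffected.

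**What to change.** In SAP 6.2.3, for non-serious unsolicited AEs flagged as after vaccination with a missing start day:

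- impute the first Rotarix PCV-free dose in the reported month, or the 1st of the month if no Rotarix dose falls in it;
- never impute a date later than the recorded end date or the visit at which the event was reported;
- state which vaccination the before/after flag refers to. The first study vaccination is the reading under which this change works alone; if the flag refers to that month's dose, the before branch needs the same change.

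Keep the current rule for SAEs and for AEs leading to withdrawal, which are collected beyond the Rotarix window, and add only the end-date and reporting-visit cap.

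The cost is a few lines of SAP text and a short derivation. Under the new rule no event with true onset on Rotarix Days 1-31 leaves the window, but that holds by construction and is not evidence of accuracy. The price lies on the other side: day-missing AEs that truly began after Day 31 and before Visit 6 will mostly be counted inside. Under the same enumeration, without the cap, that is about 89-97% of them in Co-administration at gaps of 31-36 days and 64-77% in Staggered. The error is towards counting events, which is conservative for safety, and the CSR should say so.
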